4.2 Instructions For Use, Handling and Labeling

Emdogain® and PrefGel® will be used according to the Instructions For Use (Appendix 1 and Appendix 2) containing the approved indications, contraindications, warnings, precautions and sterilization instructions:

- IFU 700019 Emdogain® (US version)
- IFU 701910 Emdogain® (German version)
- IFU 700096 PrefGel®

Emdogain® is CE marked since 1995 (0.3 ml and 0.7 ml syringes) and 2012 (0.15 ml syringe), and received FDA marketing clearance since July 2012 (PMA approval No. P930021 S013). PrefGel® is CE marked since 1997 and subject of cleared 510(k) pre-market notifications K140878 since January 2007.

Emdogain® and PrefGel® will not be used if sterile package is opened or damaged prior to use. The package will be discarded or returned to manufacturer with the enclosed syringe and cannula if this is the case. Each pre-filled syringe is intended for use in one subject only and shall not be re-sterilized or reused. Reuse of single-use devices creates a potential risk of patient or user infection. Contamination of the device may lead to injury or serious illness of the patient.

The products will be **removed from cold storage approximately 30 minutes before use**, applied at ambient temperature and within shelf life.

The plastic top of the syringe will be removed and the supplied application needle will be attached. Emdogain® will be used within 2 hours and any remaining gel will be discarded. The syringe and cannula are single use items.

The products must be used within their cleared indications.

All device deficiencies shall be reported by the Investigator to Straumann USA on the Device Deficiency Case Report Form as described under section 7.3.3.

4.3 Storage

The study products should be stored in their original container until used and its access shall be controlled.

Emdogain® and PrefGel® **must be stored in a refrigerator (2 – 8 °C / 36°-46°F)** upon arrival as indicated on the label of the packaging.

Separation of Emdogain® may occur, which is identified as a non-homogeneous gel. Homogenization of the separated material can be achieved by shaking down the gel from the top to the bottom of the syringe, turn around the syringe and repeat the procedure ten to fifteen times until homogenization returns.

4.4 Device Accountability

The Investigator must maintain an accurate and up-to-date accountability record of all study products, Emdogain® and PrefGel®, received, used, discarded (opened, but non-used) and returned during the course of the study. This information shall be recorded in the Device Accountability Record Log.

At each monitoring visit, the monitor will check the investigational device accountability for accuracy and completeness.

At the end of the study, the monitor or Straumann's delegate conducting the closeout visit will perform a final reconciliation of the device accountability (cross check between the Device Record Accountability Log, the shipments delivery notes and the acknowledgement of device receipts).

4.5 Return of Study Device

After treatment of the last subject, any remaining unopened study products at site must be returned to Straumann and acknowledged for receipt. A copy of the acknowledgement of receipt must be filed in the Investigator Site File.

4.6 Risk Analysis, Risk/Benefits

The device risk analysis and risk assessment for Emdogain® and PrefGel® was conducted according to EN ISO 14971, part of the Straumann risk management process which ensures adequate handling of risk analysis, risk evaluation, risk control and evaluation of overall residual risk acceptability. Full results are included in the Risk Management Report for Emdogain®, PrefGel® and Osteogain Version 1.0 dated 1 September 2014. Refer to the Section 7.2.6 of this protocol for a description of the anticipated adverse device effects.

Read carefully the risks associated with the investigational device and the procedures involved in its use listed in Instructions For Use in Appendix 1 and Appendix 2 under Warning and Cautions/ Precautions.

An anticipated benefit of the application of Emdogain® in combination with the minimally invasive surgical technique is the decrease of pain at treatment until 2 weeks after the surgery, as the decrease in root dentin hypersensitivity.

The identified hazards have been mitigated and the overall residual risks for the described medical devices are in the acceptable range.

In conclusion, the risks associated with the use of the Emdogain® and PrefGel® are acceptable when weighed against the benefits to the patient.

5 Study Procedures

5.1 Subject Screening and Baseline Evaluation

5.1.1 Informed Consent

The informed consent process will be conducted at Visit 1. It is the responsibility of the Principal Investigator, or a person designated by the Principal Investigator, to obtain informed consent from each subject participating in this study prior to any study related procedures. As part of the informed consent discussion with a potential subject, the Investigator or designee will provide an adequate explanation of the overall requirements/procedures of the study, purpose of the study, the nature of the planned treatment, any alternative procedures, and possible risks, complications, and benefits of the study. The Investigator or designee will also explain that the subjects are completely free to refuse to enter the study or to withdraw from the study at any time for any reason without prejudice.

The informed consent process will be approved by an Institutional Review Board (IRB) before consenting can begin. The Informed Consent Form (ICF) will be available in the primary language of the subject. This IRB approved consent form will be signed and dated by the subject and the person obtaining consent. Investigators will keep the original signed informed consent document in a secure location and a copy of the signed consent form will be given to the subject.

If new safety information results in significant changes in the risk/benefit assessment, the consent form will be reviewed and updated if necessary. All enrolled subjects will be informed of the new information, given a copy of the revised form and asked to provide consent to continue the study.

5.1.2 Inclusion and Exclusion Criteria

The inclusion and exclusion criteria will be evaluated at the screening visit. Subjects must fulfill all of the inclusion criteria and not meet any of the exclusion criteria. If this condition is not fulfilled, these patients will be considered as screen failures.

5.1.3 Medical and Dental History

Relevant medical history (e.g., allergic reactions, systemic diseases) and current medical conditions will be evaluated by the Investigator based on the information available. The information may be obtained from the subject's general physician or from oral communication with the subject.

Medical History:

If patient needs pre-medication

- Smoker: "yes" or "no"; if "yes", how many
- If patient has been treated with systemic antibiotics, if "yes"; for how long
- If patient has uncontrolled diabetes: "yes" or "no"
- If patient is immunocompromised in anyway
- If patient has history of drug or alcohol abuse
- If patient is pregnant: "yes" or "no"

Dental History:

- If patient has undergone any periodontal root planing or periodontal surgery in the last 6 months

5.1.4 Demographics

Subject demographics, including age, gender, and race/ethnicity, will be documented at the screening visit.

For race, the subject may select American Indian or Alaskan Native, Asian, Black or African American, Native Hawaiian or Other Pacific Islander, or White. For ethnicity, data will be collected on whether the subject is Hispanic or Latino.

5.1.5 Pregnancy Test

Women of child-bearing potential (women who are not surgically sterile or postmenopausal (defined as amenorrhea for >12 months)) must perform a pregnancy test (validated over-the-counter test) at Visit 1, before taking study required radiographs to confirm that the woman is not pregnant. The test result must be documented in the source data. A woman who is pregnant or planing to become pregnant at any point during the study duration cannot be enrolled in this study.

If a woman becomes pregnant during the study, a protocol deviation form should be completed. The woman should be followed for the duration of the pregnancy, without the study required radiographs, and the outcome of the pregnancy should be documented.

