Compliance	This study and any amendments will be performed according to ISO 14155:2011, ICH E6(R1) Guideline on Good Clinical Practice (GCP) 1996, and conformed to the Declaration of Helsinki (last revised Fortaleza 2013). Local legal and regulatory requirements include compliance with 21 CFR 50, 21 CFR 54, and 21 CFR 56.

Table 1 - Schedule of Assessments

	Visit 1*	Visit 2*	Visit 3	Visit 4	Visit 5	Visit 6	Visit 7	Visit 8
	Informed Consent / Screening & Baseline Visit	SURGERY (enrollment) Visit	Treatment Visit	1 Month Follow-Up Visit	3 Month Follow-Up Visit	6-Month Follow-Up Visit	9-Month Follow-Up Visit	12-Month Follow-Up Visit / Study End
Assessments	14 - 0 Days before Surgery	Day 0	Day 14-21 ± 2-3 days after Surgery	1 Month ±1 Week after Surgery	3 Months ±1 Week after Surgery	6 Months ±2 Weeks after Surgery	9 Months ±2 Weeks after Surgery	12 Months ±2 Weeks after Surgery
Informed Consent	X							
Medical & Dental History	X							
Demographics	X							
If Female, Pregnancy Test	X							
Initial Perio Exam/ Assessment of Periodontal Status	X							
Inclusion/Exclusion Criteria	X	X						
Identification & Assignment of Quadrants		X						
Full Mouth Plaque Score (FMPS)	X		X					X
Pocket Probing Depth (PPD)	X				X	X	X	X
Gingival Margin (GM)	X				X	X	X	X
Bleeding On Probing (BoP)	X				X	X	X	X
Root Dentin Hypersensitivity		X			X	X	X	X
Randomization		X						
Minimally Invasive Scaling and Root Planing (SRP) + Emdogain® First Application (as indicated by treatment assignment)		X						

	Visit 1*	Visit 2*	Visit 3	Visit 4	Visit 5	Visit 6	Visit 7	Visit 8
	Informed Consent / Screening & Baseline Visit	SURGERY (enrollment) Visit	Treatment Visit	1 Month Follow-Up Visit	3 Month Follow-Up Visit	6-Month Follow-Up Visit	9-Month Follow-Up Visit	12-Month Follow-Up Visit / Study End
Assessments	14 - 0 Days before Surgery	Day 0	Day 14-21 ± 2-3 days after Surgery	1 Month ±1 Week after Surgery	3 Months ±1 Week after Surgery	6 Months ±2 Weeks after Surgery	9 Months ±2 Weeks after Surgery	12 Months ±2 Weeks after Surgery
Supragingival Plaque Removal + Emdogain® Second Application (as indicated by treatment assignment)			X					
Pain Scale		X**	X**					
Post-treatment Oral Hygiene Instructions		X	X					
Supragingival Prophylaxis				X				
Regular Periodontal Maintenance					X	X	X	X
Radiographs (according to standard of care)	X							X
Photographs	X	X	X	X	X	X	X	X
Concomitant Medications	X	X	X	X	X	X	X	X
Adverse Events Check	X	X	X	X	X	X	X	X

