5.1.7 Adverse Event Check

At each visit the Investigator should determine if any adverse events occurred since the last study visit by speaking with the subject and reviewing any dental and medical records. These Adverse Events (AEs), along with any adverse events from the current study visit, should be documented and reported as described in Section 7. of the protocol. In addition the Investigator should evaluate the status of any ongoing adverse events throughout the study as specified in Section 7.4.

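### No pregnancy check is scheduled before the Visit 8 radiographs, about 12 months after the only pregnancy test

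*Combined protocol and SAP*

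**What the plan says.** Section 5.1.5 sets the rule. Women of child-bearing potential, meaning those neither surgically sterile nor postmenopausal, must take an over-the-counter pregnancy test "at Visit 1, before taking study required radiographs to confirm that the woman is not pregnant". The same section adds two further protections. On entry: "A woman who is pregnant or planing to become pregnant at any point during the study duration cannot be enrolled in this study". On a pregnancy arising later: "The woman should be followed for the duration of the pregnancy, without the study required radiographs".

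The scheduling is in Table 1. The row "If Female, Pregnancy Test" is marked at Visit 1 only. The row "Radiographs (according to standard of care") is marked at Visit 1 and again at Visit 8, whose window is "12 Months ±2 Weeks after Surgery". Section 6.2 (Visit 1) lists both the test and the radiographs. Section 6.9 (Visit 8) lists radiographs but neither a pregnancy test nor a question about pregnancy.

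Section 5.3.8 allows peri-apical, panoramic or cone beam images according to each clinic's practice, and words the baseline and 12-month time points as a preference.

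**The concern.** The stated purpose of the test is to protect against irradiating a pregnant participant, and a second set of images is scheduled about a year after the first. A negative result at Visit 1 says nothing about pregnancy status at Visit 8. Section 5.1.5 has a rule for withholding radiographs once a pregnancy is known, but the plan schedules no step after Visit 1 to find one.

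A site that followed Table 1 and section 6.9 to the letter could therefore take the Visit 8 image in a woman with an unrecognised pregnancy and still be fully compliant. What is at stake is participant safety. Clinical attachment level and the other endpoints are untouched.

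**Working it through.** The plan gives no figure on this point, so there is nothing to reproduce. The check has three parts.

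**1. Could anything else scheduled detect a pregnancy before the Visit 8 image?**

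| Provision | When it applies | Detects an unrecognised pregnancy at Visit 8? |
|---|---|---|
| Pregnancy test (5.1.5, Table 1) | Visit 1 | No, not repeated |
| Medical history item "If patient is pregnant" (5.1.3) | Visit 1 in Table 1 | No, not repeated |
| Eligibility review, with pregnancy an exclusion (3.7.2) | Visits 1 and 2 | No, not repeated |
| Bar on women planning pregnancy (5.1.5) | Entry | No, does not cover unplanned pregnancy |
| Concomitant medication update (5.1.6) | Every visit | No, might reveal a known pregnancy |
| Adverse event check, made "by speaking with the subject and reviewing any dental and medical records" (5.1.7) | Every visit | No, pregnancy is not named; might reveal a known one |
| Withholding rule (5.1.5) | Once a pregnancy is known | No, acts only after detection |

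After Visit 1, Table 1 schedules radiographs only at Visit 8. The withholding rule can therefore bear on no other scheduled image, so the protocol already treats the Visit 8 image as one to omit in pregnancy.

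**2. How old is the test result by then?**

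Inputs: Visit 1 falls 0 to 14 days before surgery, and may share an office visit with surgery (Table 1 and section 6.3). Visit 8 is 12 months after surgery, plus or minus 14 days (Table 1 and section 6.1). Twelve months is taken as 365 days.

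Interval = days from Visit 1 to surgery + days from surgery to Visit 8.

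- Shortest: 0 + (365 − 14) = 351 days; 351 / 7 = 50.1 weeks.
- Longest: 14 + (365 + 14) = 393 days; 393 / 7 = 56.1 weeks.

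**3. How many participants could be affected?**

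Inputs: 50 subjects (section 3.5) and dropout of up to 15% (section 8.1). The documents give neither the number of women of child-bearing potential nor a rate of unrecognised pregnancy. The rate is assumed to be 0.1% to 1% per woman at the visit.

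- Subjects reaching Visit 8: at most 50; with 15% dropout, 50 × 0.85 = 42.5, so about 42.
- Ceiling on expected unrecognised pregnancies, treating all 50 as women of child-bearing potential: 50 × 0.001 = 0.05 to 50 × 0.01 = 0.5.

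The true figure is lower, because the population is of both sexes and aged 18 to 85.

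**The case against.** The strongest reply is that the Visit 8 image is largely left to clinic practice. Section 5.3.8 defers to each site's routine and only prefers a 12-month image, and that routine may well include asking about pregnancy. So the documents show that the protocol schedules no check, not that none would take place. That distinction stands, and it is one reason to rank the point low. It does not close the gap: the same softened wording covers the Visit 1 images, and there the protocol still required a test.

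A second reply is that the Visit 1 test also serves eligibility, so part of its purpose does not recur at Visit 8. This is fair, but section 5.1.5 names the radiographs as the reason for the test, and that reason does recur.

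A third is that a documented question would be lighter than a test. A question would help with a known but unreported pregnancy. It cannot find one the woman is unaware of, and that is the case left over.

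Finally, the consequence of each event is not quantified, because the documents give no fetal dose or risk from dental imaging. That also stands.

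**Conclusion.** The concern holds. The protocol requires a pregnancy test before the first study radiographs and schedules no check of any kind before the second, 351 to 393 days later. The exposure is limited to unrecognised pregnancy at a single visit. The expected count is at most 0.05 to 0.5, and this rests on an assumed rate of 0.1% to 1% and on the deliberately extreme premise that all 50 subjects are women of child-bearing potential; in practice it is well below one. There is no effect on the primary analysis or any other endpoint. This is a minor safety improvement that could be made, not a defect that threatens the study.

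One limit concerns timing. The synopsis planned for follow-up to end by December 2017, while the protocol version is dated 29 March 2018. The documents do not say whether any Visit 8 was still to come.

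**What to change.** In section 5.1.5, section 6.9 and Table 1, require the same over-the-counter test at Visit 8 for women of child-bearing potential, before any radiograph taken at that visit, with the result recorded in the source data. If it is positive, withhold the radiograph and follow the pregnancy as section 5.1.5 already describes. If no radiograph is taken at Visit 8, no test is needed.

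The cost is one mark in Table 1, one line in section 6.9 and a short edit to section 5.1.5. It adds at most one test per subject reaching Visit 8, and fewer than 50 in all, since men, postmenopausal women and surgically sterile women need none. No endpoint or analysis changes. If no Visit 8 remains, the correction should go into the larger trial that section 2 foresees.

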5.1.6 Concomitant Medication

Concomitant medication, procedures, and supportive therapies will be recorded at the screening visit. Any changes in the concomitant medications, procedures, and supportive therapies must be documented at each study visit until the end of the study.

5.1.7 Adverse Event Check

At each visit the Investigator should determine if any adverse events occurred since the last study visit by speaking with the subject and reviewing any dental and medical records. These Adverse Events (AEs), along with any adverse events from the current study visit, should be documented and reported as described in Section 7. of the protocol. In addition the Investigator should evaluate the status of any ongoing adverse events throughout the study as specified in Section 7.4.

5.2 Treatment Procedures

The treatment workflow is graphically presented in Appendix 3 and starts from Visit 2 – Surgery Visit.

5.2.1 Selection and Assignment of Quadrants

The inclusion and exclusion criteria will be reviewed (Section 3.7.1 and 3.7.2). If the subject remains eligible, randomized treatment assignment of a quadrant (test or control), will be done via randomization envelopes. At Visit 2, the Investigator or designee will open a sealed randomization envelope. The randomization envelope will identify the treatment assignment for the right and left quadrants, both in the same arch of the eligible patient. **Randomization envelopes must be open in sequential order.**

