	Appendix 3 – Instructions For Use IFU 700096 - Pref-Gel®	92
	Appendix 3 – Treatment Workflow	96
	Appendix 4 – Visual Analog Scale (VAS)	98
	Appendix 5 – Declaration of Helsinki	101

1 Background and Rationale

The goal of regenerative periodontal therapy is the reconstruction of lost periodontal structures. Results from preclinical and clinical studies have shown that Emdogain® successfully promotes periodontal wound healing and regeneration, when used in conjunction with periodontal open flap surgery¹. Although Emdogain® has been proven successful to effectively promote periodontal regeneration as part of surgical procedures attempts to use the product for periodontal regeneration as part of minimally invasive surgery (i.e. flapless) procedures remain inconclusive and controversial or do not allow a definite conclusion on the effectiveness.^{1, 2, 3, 4, 5, 6, 7, 8, 9, 10} Although the majority of reports does not support the use of Emdogain® in flapless periodontal procedures, few reports like the one of Wennström et al. indicate a potential effect of the product in flapless periodontal procedures¹⁰. Specifically the authors have reported that Emdogain® provides an advantage in the early wound healing after flapless periodontal debridement.

A more thorough review of the available literature suggests that all attempts to establish the use of Emdogain® in flapless methods have lacked a systematic and standardized approach. In particular the preconditions as well as the details of the clinical workflow need to be carefully defined in order to analyze the success of regenerative procedures using Emdogain® in a flapless application. With this regards thorough debridement of the root/dentin surface but also removal of granulation tissue might be considered as a precondition for Emdogain® mediated regeneration of the periodontal tissues and periodontal attachment. As a consequence a defined and validated workflow is estimated to be necessary in order to achieve this goal. According to our knowledge such a systematic approach, which is considered to be necessary has not been applied yet to analyze the potential of Emdogain® in flapless periodontal procedures.

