3.3 Study Treatments

The workflow consists of:

Baseline evaluation:

The initial periodontal examination is conducted at the Visit 1 and includes a complete periodontal charting, including Pocket Probing Depth (PPD), Gingival Margin (GM), Bleeding on Probing (BoP), and Full Mouth Plaque Score (FMPS). This examination will be used to determine eligibility for the study based on inclusion/exclusion criteria (Section 3.7.1 and Section 3.7.2). Also, these are the baseline data used for the statistical analysis.

Treatment:

After qualification for the study, the subject will be randomized and treated with minimally invasive Scaling and Root Planing (SRP). An initial application of Emdogain® is performed during the SRP treatment for one quadrant (test). SRP alone will be performed in the contralateral quadrant (control). In addition, PrefGel® is applied on the test quadrant only (prior to the initial application of Emdogain®).

Based on the reported literature on how long Emdogain® remains in periodontal pockets^{11,10} a second application will be carried out 2-3 weeks after the initial Emdogain® application for the test quadrant to ensure longer presence of Emdogain® in the defect. Postoperative treatment is detailed in Section 5.2.3.

Re-evaluation and Follow-Up:

At 3 months, 6 months, 9 months, and 12 months after the initial application of Emdogain®, re-evaluations will be carried out in order to identify residual pockets that are indicated for perio-surgery (PPD ≥ 5 mm). This study design, including a dual application of Emdogain®, clearly aims to differentiate this treatment workflow from the approaches that have been reported in the literature.

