5.2.2 Surgery - Minimally Invasive Scaling and Root Planing and Emdogain® First Application

Patients that have been randomized and have scaling and root planing with Emdogain® treatment during Visit 2 are considered enrolled in the study. Each subject will receive local anesthetic and be treated in one visit with a sequence of steps defined by the treatment assignment:

- Test treatment: For the quadrant assigned to scaling and root planing + Emdogain® the following steps should be conducted for treatment: scaling and root planing, control of bleeding, application of PrefGel® (until there is clear overflow from the pocket) to remove any residual smear layer for 2 minutes, irrigation with sterile saline thoroughly, and application of Emdogain® starting apically and advancing coronally until there is clear overflow from the pocket.

- Control treatment: For the contralateral quadrant, assigned to scaling and root planing alone, the following steps should be conducted at the same visit as the test treatment: scaling and root planing and control of bleeding.

Mechanical debridement will be carried out in the manner commonly performed by the clinician (e.g., hand instrumentation, ultrasonic scalers with diamond tips). No antimicrobial agents or techniques (antibiotics or antiseptics, photodynamic therapy) will be applied during treatment. No vasoconstrictors (other than 1:100 000 or 1:200 000 epi in local anesthetic) or hemostatic agents will be used in surrounding soft tissues or pockets. Bleeding will be stopped by conventional techniques as much as possible. No sutures or periodontal dressings will be applied.

In order to standardize treatment across centers, only loupes or a microscope can be used as an assistive visual aid for debridement and removal of calculus from defects.

Other quadrants not being evaluated in the study should be treated according to standard practice.

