5.3 Outcome Assessments

The following measurements will be taken by the same examiner throughout the study.

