6.1 Visit Windows

Subjects need to be seen within the following windows:

Visit #	Visit Name	Visit Window
Visit 1	Informed Consent/Screening & Baseline Visit	14 - 0 Days before enrollment
Visit 2	Final Screening Randomization Minimally Invasive Scaling and Root Planing and Emdogain® First Application	RANDOMIZATION AND SURGERY - Point of enrollment Day 0
Visit 3	Supragingival Plaque Removal and Emdogain® Second Application	2-3 Weeks \pm 2-3 Days
Visit 4	Regular Periodontal Maintenance	1 Month \pm 1 Week
Visit 5	3-Month Follow-up Visit	3 Months \pm 1 Week
Visit 6	6-Month Follow-up Visit	6 Months \pm 2 Weeks
Visit 7	9-Month Follow-up Visit	9 Months \pm 2 Weeks
Visit 8	12-Month Follow-up Visit	12 Months \pm 2 Weeks

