6.2 Visit 1 – Screening & Baseline Visit

This visit should be completed within 14 days prior to the Surgery Visit (Visit 2). An initial evaluation will be conducted to determine whether the subject meets the study inclusion and exclusion criteria.

The following procedures and assessments will be performed and recorded at the screening visit:

- Informed consent
- Medical & Dental history

- Demographics
- Pregnancy Test
- Inclusion/exclusion criteria
- Initial Periodontal Examination and Assessment of Periodontal Status
- Collection of baseline clinical measurements:
 - Pocket Probing Depth
 - Gingival Margin
 - Bleeding on Probing
 - Full Mouth Plaque Score
- Radiographs
- Photographs
- Concomitant Medications
- Adverse Events check

6.3 Visit 2 – Minimally Invasive Scaling and Root Planing and Emdogain® First Application (SURGERY)

Visit 2 needs to be completed within 14 days from the Screening & Baseline Visit. It is possible to conduct Visit 1 and Visit 2 at the same office visit.

The following will be conducted during this visit:

- Final review of inclusion/exclusion criteria and determination of subject eligibility.
- Identification of the contralateral quadrants and treatment assignment
- Root Dentin Hypersensitivity at the study teeth
- Randomization (if subject meets all eligibility criteria).
- Minimally invasive scaling and root planing, control of bleeding, application of PrefGel®, irrigation with sterile saline, and first application of Emdogain® for teeth treated in test quadrant.
- Scaling and root planing and control of bleeding for teeth treated in control quadrant.
- Pain scale completion by the patient

- Post treatment oral hygiene instructions
- Photographs
- Concomitant Medications
- Adverse Events check

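### The protocol places randomization before scaling and root planing and describes no operator masking, so the operator can know the Emdogain quadrant while debriding both sides

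*Combined protocol and SAP*

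**What the plan says.** Section 5.2.1 gives the mechanism: "At Visit 2, the Investigator or designee will open a sealed randomization envelope". On what it discloses: "The randomization envelope will identify the treatment assignment for the right and left quadrants, both in the same arch of the eligible patient".

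The order relative to debridement comes from other places:

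- Section 3.3: "After qualification for the study, the subject will be randomized and treated with minimally invasive Scaling and Root Planing (SRP".
- Section 6.1, Visit 2 row: "Final Screening Randomization Minimally Invasive Scaling and Root Planing and Emdogain® First Application".
- Section 6.3 and Table 1 list randomization immediately above the SRP entry.
- Section 5.2.2 makes the sequence of steps depend on the assignment, with SRP as the opening step in each quadrant.

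On how debridement is done, section 5.2.2 says: "Mechanical debridement will be carried out in the manner commonly performed by the clinician". It gives instruments only as examples. It restricts visual aids to loupes or a microscope and bars antimicrobials, hemostatic agents, sutures and dressings. It sets no duration and no criterion for when a root surface is clean enough.

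Section 1 says that "thorough debridement of the root/dentin surface but also removal of granulation tissue might be considered as a precondition" for Emdogain-mediated regeneration. Section 3.1 describes the design without any masking.

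**The concern.** In a split-mouth trial, the patient's own control quadrant carries the comparison. It is fair only if everything other than the assigned treatment is done alike on both sides. SRP is a manual step done by one operator on both sides at the same visit. If the operator already knows which side is the test side, the effort spent on each side can differ, deliberately or not. The background supplies a motive, since it suggests that the device may need a thoroughly cleaned root.

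At stake is the primary objective, the test-control difference in CAL, together with probing depth and bleeding on probing. Better debridement could improve all three without any contribution from Emdogain.

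**Working it through.** No figure in the plan can be reproduced on this point, so the check is one of sequence and then of logic.

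**1. Is the envelope opened before SRP?** No single sentence says so. The evidence is:

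| Place | What it shows | Strength |
|---|---|---|
| 5.2.1 | Opened at Visit 2 | Gives the visit only |
| 3.3 | Randomized, then treated with SRP | Order by wording |
| 5.2.2 | Steps follow from the assignment; SRP comes first in a quadrant already assigned | Strongest |
| 6.1 | Randomization named ahead of SRP | Order by listing |
| 6.3 and Table 1 | Randomization directly above SRP | Order by listing; neither is strictly chronological |

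All point the same way, and none places SRP first. The treatment workflow figure in Appendix 3 is not shown in the text available and could not be checked.

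**2. Does anything keep the result from the operator?** A designee may open the envelope, but nothing says that the result is withheld from the person who debrides. The description of treatment in 5.2.2 presupposes that it is known.

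**3. Does the operator need the assignment during SRP?** From section 5.2.2:

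- Test: SRP, bleeding control, PrefGel, saline irrigation, Emdogain.
- Control: SRP, bleeding control.

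The first two steps are identical. The assignment is needed only from PrefGel onward.

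**4. What does the order do to the estimate?** For one patient, write the test-minus-control difference in CAL change as

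D = δ + b + error,

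where δ is the effect of the assigned test-quadrant steps and b is the contribution of any difference in debridement between the two sides.

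- Assignment known during SRP: b may depend on the assignment. The mean of D estimates δ + E(b). If E(b) is not zero, more patients do not reduce it.
- Assignment opened after SRP in both quadrants: debridement is already fixed for right and left. Assuming that each side is equally likely to be test (the protocol says randomly assigned but gives no ratio), the right-left difference r enters as +r or −r with probability 1/2 each. So E(b) = ½r − ½r = 0.

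Under the first order, δ and E(b) cannot be told apart. The reason is that debridement effort would follow allocation, not that both sides belong to the same patient. The protocol names no measure of debridement time or completeness that would reveal a difference.

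**5. Can E(b) be sized?** No. The documents give no debridement times, no effect of debridement time on CAL and no standard deviation for the paired difference. The direction is not fixed either: the motive in section 1 favours the test side, but an operator might also compensate on the control side.

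**The case against.** The strongest reply is that this is a pilot. Section 8.1 describes it as a step toward a standardized workflow, section 2 as a controlled case series giving a first indication, and section 8.3.1 plans descriptive statistics for the primary endpoint. Section 8.3 relies on standardized procedures and investigator training, and section 5.2.2 restricts visual aids and agents and requires both quadrants to be treated at one visit. The operator will be unmasked anyway once PrefGel is applied.

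Much of this is true, but it does not remove the problem. Descriptive means carry the same bias as a test. The restrictions do not limit time or thoroughness. Unmasking at PrefGel comes after debridement. Section 2 also calls the study pivotal and says that its findings will shape a larger trial.

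A second reply concerns dates. The synopsis planned enrollment through December 2016 and follow-up through December 2017, while the text is Version 5.0 of 29 March 2018. If those plans were met, the sequence can no longer be changed for these patients. That stands, and it decides which remedy applies.

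Three stronger readings are tempting and should not be drawn:

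- *That the background makes thorough debridement a requirement.* It says only that it might be considered one.
- *That debridement will in fact be better on the test side.* The documents show opportunity and a possible motive, and the absence of masking is itself inferred from silence.
- *That the bias is a stated share of the expected effect.* Such a figure would divide an assumed shift by CAL differences from the table in Appendix 1. Those are 0.3 to 0.6 mm in the full split-mouth groups but 1.3 mm in a 10-patient subset with pockets over 8 mm. They come from comparisons with surgery in 1- or 2-wall defects, and section 1 calls the flapless evidence inconclusive.

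Finally, section 5.3 says "The following measurements will be taken by the same examiner throughout the study" without stating whether that examiner is masked. That is a separate question with its own remedy and is not used as support here.

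**Conclusion.** The point holds as an avoidable opportunity for performance bias. On the sections that imply an order, the operator can know the allocation during SRP and bleeding control, when neither treatment sequence requires it. Any resulting difference would be confounded with allocation and could not be separated from an Emdogain effect on CAL, probing depth or bleeding.

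Its size cannot be estimated from the documents, so I give no millimetre figure or percentage. The conclusion rests on two assumptions: that the unseen workflow figure does not reverse the order, and that no masking arrangement exists outside the protocol. This is a recommended, low-cost improvement. It is not evidence that the comparison has been distorted.

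**What to change.** Amend sections 3.3, 5.2.1, 5.2.2, 6.1, 6.3 and Table 1 together, and check the Appendix 3 workflow against them, so that all give one order at Visit 2:

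1. Confirm eligibility and fix the study teeth and sites.
2. Complete SRP and bleeding control in both quadrants.
3. Open the next envelope in sequence.
4. Carry out the remaining assigned steps in the test quadrant.

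Each quadrant's own steps and their order stay as they are. The change also fits section 5.4.1, which counts a subject as enrolled only once randomized and treated with Emdogain.

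Add two case report form fields: the time of envelope opening, and SRP minutes for each quadrant. Keep the assignment off the follow-up probing forms. A separate examiner is not part of this change.

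The cost is protocol wording and two fields. The downside is that bleeding control may need rechecking in the quadrant debrided first. This should be done in both quadrants so that it does not create a new asymmetry; it adds a few minutes per patient.

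If all Visit 2 procedures are already complete, state in the Clinical Investigation Report that the operator was not masked during debridement, treat this as a limitation of the test-control comparison, and correct the workflow before the follow-on trial.
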